#### Neurologic Acute Toxicity

Because radiation therapy is directed to the craniospinal axis, a neurologic acute toxicity rate  $\leq 10\%$  is considered acceptable. We will assume a beta (1,5) prior, which is information equivalent to acute neurologic toxicity in one of 6 treated patients. If the number of patients with neurologic acute toxicity equals or exceeds the number in the table, then termination will be considered as it is likely that the toxicity rate is  $\geq 10\%$ , as noted by the Bayesian posterior probabilities.

Bayesian Rule for Neurologic Acute Toxicity					
Patients treated 3 6 9 1					
				2	

Patients who experience acute toxicity	1	1	2	2	
Posterior Prob[toxicity rate	0	0	0	0	
>10%]		7	Q	. 7	
	1	0	4	6	
Action	To	erminate e	nrollment		

### 7.1.4 Statistical Analyses

Feasibility. The initial target sample size of 12 patients will be revised to 12 additional base of skull patients to be treated with pencil beam protons and evaluated for feasibility by the new definition. It is anticipated that up to 5 additional spine patients may be enrolled. So the total enrollment after this amendment will be up to 17 patients (12 base of skull and 5 spine). The statistical analysis will calculate the posterior probability that the feasibility rate is >90%. This analysis will be conducted 2 ways: based on all 26 patients treated and on all 17 patients treated after the modification. The definition of infeasibility will be that which was current when the patient enrolled on the trial. There will be no retroactive re-grading of infeasibility in the base of skull patients.

Acute Toxicity. All toxicities observed within 90 days from start of therapy will be graded by CTC Version 4.0 and tabulated. Special attention is paid to neurologic toxicity.

Late Toxicity. All toxicities observed later than 90 days from start of therapy will be graded by the CTCAE version 4.0 and tabulated.

Progression-free and overall survival will be estimated by the survival analysis methods. It is most likely that these time-to-event outcomes will be summarized as part of the phase II study.

Fatigue is scored on a 10-point scale based on the Brief Fatigue Inventory Questionnaire. At each time point, the BFI score will be summarized by mean and standard deviation, and plotted over time. We will examine the plots for the expected worsening of function in the 6-12 months post-radiation and gradual improvement from 12-24 months. The fatigue scores will be summarized in detail in the phase II study.

Neurocognitive function (FACT-Br) will be summarized by descriptive statistics and scatter plots. It is most likely that the neurologic outcomes will be summarized as part of the phase II study.

Estimation of Event Rates. The table below displays the 90% exact binomial confidence

intervals based on 12 patients treated.

intervals ous	ed on 12 patients	i catea.			
No. of	%	90%	No. of	%	90%
Events		exact	Events		exact
		CI			CI
0	0.0	17.5*	7	58.3	31.5,
					81.9
1	8.3	.43,	8	66.7	39.1,
		33.9			87.7
2	16.7	3.0,	9	75.0	47.2,
		43.8			92.8
3	25.0	7.2,	10	83.3	56.1,
		52.7			97.0
4	33.3	12.3,	11	91.7	66.1,
		60.9			99.6
5	41.7	18.1,	12	100.0	82.5*
		68.5			
6	50.0	24.5,		* 90%	1-sided CI
		75.5			

#### 7.2 PHASE II STUDY

Once feasibility and safety are established in the first 12 patients, then the phase II study will commence.

#### 7.2.1 Design and Objectives.

Proton therapy at standard doses is not expected to improve clinical outcome but will likely reduce fatigue and toxicity. The purpose of the phase II study is to characterize toxicity rates and to summarize fatigue scores at time points during and post-radiation. Progression-free survival will also be estimated. There will be no early stopping in this phase of the study. Outcomes from the initial 12 patients will be included in this evaluation. An additional 38 patients will be enrolled on the phase II study, for a phase II study total of 50 patients. We may have to screen/enroll up to 50 subjects to reach the goal of 38 additional patients in the phase II portion of the trial.

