#### 7.1.3 Rules for Early Termination

Bayesian probability calculations will be employed to define rules of early termination for feasibility and safety. The tables below indicate termination rules after groups of 3 patients have been treated, although the Bayesian probability of an event may be calculated at any time during the trial. Hundreds of patients with certain types of cancer have undergone radiation therapy with protons. Thus, we will assume a modest amount of "prior" feasibility and safety data for proton for our Bayesian calculations. We will assume prior information equivalent to that of 6 treated patients, which is commonly required to establish safety in a standard 3+3 Phase-I trial design.

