#### **Feasibility**

A feasibility rate  $\geq 90\%$  is considered acceptable. We will assume a beta (5,1) prior, which is information equivalent to feasibility established in 5 of 6 treated patients. If the number of patients in whom proton is deemed feasible is less than or equal to the number in the table below then termination will be considered as it is highly unlikely that the feasibility rate is  $\geq 90\%$ , as noted by the Bayesian posterior probabilities.

D ' D 1	C D '1 '1'	• ,				
Bayesian Rule	for Feasibili	ıty				
Patients treated in each stratum	3	6	9	1		
				2		
Patients in whom proton is	1	4	6	9		
feasible						
Posterior Prob[feasibility rate	0	0	0	0		
>90%]		•	•	•		
	0	0	0	0		
	4	9	4	8		
Action	Т	Terminate enrollment				

Acute toxicity will be divided into 2 categories to best characterize toxicities in this disease. Non-Neurologic Acute Toxicity

Because proton therapy is expected to spare normal tissues, a non-neurologic acute toxicity rate  $\leq 20\%$  is considered acceptable. We will assume a beta (1,5) prior, which is information equivalent to toxicity in of treated patients. If the number of patients with non-neurologic acute toxicity equals or exceeds the number in the table, then termination will be considered as it is likely that the toxicity rate is >10%, as noted by the Bayesian posterior probabilities.

Bayesian Rule for Non-Neurologic Acute Toxicity						
Patients treated	3	6	9	1		
				2		
Patients who experience acute	2	2	3	4		
toxicity						
Posterior Prob[toxicity rate	0	0	0	0		
>20%]			•			
	8	6	7	7		
	0	2	0	6		
Action	Te	Terminate enrollment				

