#### 7.2.4 Statistical Analyses.

Analyses of acute and late toxicity and fatigue will be completed within 1 year of completion of accrual. Time-to-event outcomes and long term longitudinal measurements of fatigue and neurocognitive function will be analyzed 2-3 years after completion of accrual. Descriptive analyses and subset analyses are likely. The purpose of these subset analyses is hypothesis generation. Subgroup analyses will likely describe time-to-event outcomes by histology (e.g., chordoma or chondrosarcoma) and extent of surgery (e.g., biopsy only, partial debulking, and maximal debulking). They will produce estimates of clinical outcomes, to aid in the design of future clinical trials.

Acute and Late Toxicity. All acute and late toxicities will be graded by CTCAE Version 4.0 and tabulated. Toxicity rates and 95% confidence intervals will be calculated. The maximum half-width of the 95% confidence interval is  $\pm 14\%$  based on 50 patients.

Time-to-Event Outcomes. Trials of chordomas and chondrosarcomas which combine proton with photon, have demonstrated 5-year progression-free survival rates (i.e., free of local failure) of 60-80%. We do not expect the 5-year PFS rate to be much different with protons. Progression-free and overall survival and time to local failure, will be estimated by the Kaplan-Meier method. Median and 5-year estimates and 95% confidence intervals will be calculated.

Fatigue (Brief Fatigue Inventory, BFI) & Neurocognitive function (FACT-Br) will be summarized by mean and standard deviation calculated and plotted over time. We will examine the plots for the expected worsening of function in the 6-12 months post-radiation and gradual improvement from 12-24 months. Pre- and post-treatment comparisons at a primary time point (e.g., at 24 months post-radiation when function should have recovered) will be evaluated by Student's paired t-test or nonparametric Wilcoxon signed ranks test. A general strategy to assess trends over time in longitudinal data is to employ linear mixed effects models, which can account for the impact of covariates such as anti-seizure medication and baseline performance status. The BFI can also be categorized as mild (1-3), moderate (4-6) and severe (7-10). The rates of patients in the severe category will be estimated at each time point. Of primary interest are the rates at 12 and 24 months post-treatment.

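### The Phase II acute toxicity rates pool 12 patients already screened for low acute toxicity, so the pooled rates run modestly low once Phase II has opened

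*Combined protocol and SAP*

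**What the plan says.** Section 7.2 makes Phase II conditional on the feasibility cohort: "Once feasibility and safety are established in the first 12 patients, then the phase II study will commence". Section 7.1.3 gives the monitoring scheme: "The tables below indicate termination rules after groups of 3 patients have been treated". Its two toxicity tables concern acute toxicity only. The non-neurologic bounds are 2, 2, 3 and 4 patients with toxicity at 3, 6, 9 and 12 treated. The neurologic bounds are 1, 1, 2 and 2. When a bound is reached, the text says that termination is to be considered, not that it follows automatically.

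Section 7.2.1 states the aim of the second stage, "The purpose of the phase II study is to characterize toxicity rates and to summarize fatigue scores", and its size: "An additional 38 patients will be enrolled on the phase II study, for a phase II study total of 50 patients". It then pools the stages: "Outcomes from the initial 12 patients will be included in this evaluation". Section 7.2.4 says only "Toxicity rates and 95% confidence intervals will be calculated", with a maximum half-width of 14 points for 50 patients. It plans no separate report of the later 38, no stage-adjusted estimate, and no note that 12 of the 50 were screened on the outcome being estimated.

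**The concern.** A trial that reaches Phase II is one in which the first 12 patients had few acute toxicities. Averaging those 12 with 38 unscreened patients, as if all 50 were an unselected sample, pulls the reported rate below the true one. The error favours the treatment and grows with true toxicity. Describing toxicity rates is a stated purpose of Phase II, and Section 7.2.4 intends its estimates to help in designing later trials. A later designer should be able to see how much of the reported rate comes from screened patients.

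**Working it through.** **The plan's own figures.** The half-width for 50 patients is 1.96 × √(0.25/50) = 13.9 points, which matches the stated 14. With the beta(1,5) prior, the feasibility-stage posterior probabilities also reproduce: 0.80, 0.62, 0.70 and 0.76 (non-neurologic), and 0.81, 0.70, 0.84 and 0.76 (neurologic). The bounds used below are therefore the intended ones.

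**Assumptions.** The bounds bind, each toxicity type is gated separately, and the 38 later patients are unselected. The documents give no true rates, so a range is shown. If m is the expected number of events in the first 12 given a pass, and p is the true rate, the expected pooled rate is (m + 38p)/50.

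**Neurologic gate.** Passing requires no event in patients 1–6 and at most one in patients 7–12. With q = 1 − p:

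- P(pass) = q⁶ × (q⁶ + 6pq⁵)
- m = 6p/(q + 6p)

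At p = 10%, P(pass) = 0.5314 × 0.8857 = 0.47 and m = 0.6/1.5 = 0.40. The first 12 average 0.40/12 = 3.3%, and the pooled rate averages (0.40 + 3.8)/50 = 8.4%. At p = 20%, m = 1.2/2.0 = 0.60, giving (0.60 + 7.6)/50 = 16.4%.

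**Non-neurologic gate.** Passing requires at most 1 event by patient 6, at most 2 by patient 9 and at most 3 by patient 12. Carrying the binomial probabilities through these looks at p = 20% gives 0.0687, 0.2062, 0.2190 and 0.0977 for 0, 1, 2 and 3 events at patient 12. These sum to 0.59, the chance of passing. Then m = (0.2062 + 2 × 0.2190 + 3 × 0.0977)/0.5916 = 1.58. The first 12 average 13.2%, and the pooled rate averages (1.58 + 7.6)/50 = 18.4%.

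| Type | True rate | P(pass) | First 12, given pass | Pooled 50 | Bias (points) |
|---|---|---|---|---|---|
| Neurologic | 5% | 0.71 | 2.0% | 4.3% | −0.7 |
| Neurologic | 10% | 0.47 | 3.3% | 8.4% | −1.6 |
| Neurologic | 20% | 0.17 | 5.0% | 16.4% | −3.6 |
| Non-neurologic | 10% | 0.87 | 8.0% | 9.5% | −0.5 |
| Non-neurologic | 20% | 0.59 | 13.2% | 18.4% | −1.6 |
| Non-neurologic | 30% | 0.31 | 16.7% | 26.8% | −3.2 |

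**Looser gate.** If only the 12-patient look binds, the bias is −1.3 points (neurologic, true 10%) and −1.1 points (non-neurologic, true 20%).

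**Phase II bounds added.** If the counts printed in Section 7.2.3 also bind, then among trials reaching 50 patients a true 10% neurologic rate averages 7.7% pooled and 9.2% in the later 38. A true 20% non-neurologic rate averages 16.5% and 17.9%.

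**Intervals.** Exact 95% interval coverage given a pass is 0.983 (neurologic, 10%) and 0.966 (non-neurologic, 20%). At a true neurologic rate of 20% it is 0.936, and the chance that the whole interval lies below the truth is 6.3%, against 1.8% with no gate.

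**The case against.** The strongest reply is that the effect is small where it is most likely to arise. At the protocol's own acceptable limits, 1.6 points is 0.8 of one event in 50, against a half-width of 14 points. Exact intervals keep at least 95% coverage there. Pooling also has the smaller root mean squared error: 4.2 against 4.9 points for the 38 alone (neurologic, 10%), and 5.5 against 6.5 (non-neurologic, 20%). The material distortions need true neurologic rates of 20–30%, at which the chance of passing the gate is only 17% to 5%. Phase II is descriptive and tests no toxicity hypothesis. All of this stands, and it is why the pooled estimate should stay.

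A reader might infer more than the documents support, in four ways:

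- **That Phase II can exist only if no bound was reached.** Termination is only to be considered, so a bound may be overridden, which shrinks the bias. Section 7.2 still requires safety to be established, so some selection remains.
- **That every Phase II toxicity rate is affected.** Late toxicity has no bound. Any effect on it would come through correlation with acute toxicity, which the documents do not quantify.
- **That the bias scales with the size of the gating cohort.** Extending the gate to the 25-patient look with the printed bounds gives −1.8 (neurologic, 10%) and −2.3 points (non-neurologic, 20%). Proportional growth from 12 to 25 would give about 1.6 × 25/12 = 3.3 points.
- **That a standard unbiased sequential estimator, the UMVUE, is the cure.** It is unbiased over all trials, including those that stop, not given a pass. It equals the expected rate in the first 3 patients given the final count. Every trial passing the neurologic bounds has 0 of 3, so it reports 0% whatever happens later. For a true non-neurologic rate of 20% it averages 9.4% given a pass, far worse than 18.4%.

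**Conclusion.** The point holds for acute toxicity and is minor. Given that Phase II opens, the pooled rate is biased low by about 1.6 points at the protocol's acceptable limits if all four looks bind, and by 1.1 to 1.3 points if only the 12-patient look binds. The bias reaches 3.6 points at a true neurologic rate of 20% and 3.2 points at a true non-neurologic rate of 30%. The documents do not support calling the intervals invalid at acceptable rates, or discarding the first 12.

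Two unsettled matters limit how far the 38-patient figure can be taken as free of selection. Section 7.2.1 says Phase II has no early stopping, while Section 7.2.3 prints stopping tables for it; if those apply, the 38 are themselves selected. Also, Sections 7.1.4 and 7.3 revise the feasibility target to 12 additional base of skull patients plus up to 5 spine patients, and Section 7.1.4 counts 26 treated in all. It is therefore unclear who the initial 12 are.

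**What to change.** In Section 7.2.4:

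- Keep the pooled 50-patient acute toxicity rates and intervals.
- Report beside them the rates and 95% intervals for the 38 patients enrolled after the gate, separately for neurologic and non-neurologic toxicity.
- State that the pooled figures include patients selected by the safety gate.
- Do not substitute the UMVUE, and do not make the 38-patient figure the sole basis for conclusions.

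Elsewhere, reconcile Section 7.2.1 with Section 7.2.3 on Phase II stopping. If bounds apply in Phase II, say that the 38-patient rate is also somewhat low. Define which patients are the initial 12 after the amendment, and so which patients count as enrolled after the gate.

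The cost is one extra table row for each toxicity type and a wider interval in that row: a maximum half-width of 1.96 × √(0.25/38) = 15.9 points against 13.9. No extra patients or data are needed.

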#### 7.2.2 Endpoints. Same as in 7.1.2

Acute Toxicity. Late toxicity. Fatigue & Neurocognitive function. Progression-free and overall survival.

### 7.2.3 Rules for Early Termination; continuation of rules as in 7.1.3

#### Non-Neurologic Acute Toxicity

If the number of patients with non-neurologic acute toxicity equals or exceeds the number in the table, then termination will be considered as it is likely that the toxicity rate is >20%, as noted by the Bayesian posterior probabilities.

Bayesian Rule for Non-Neurol	logic A	Acute Toxicit	У	
Patients treated	1	2	3	4

Version: 04/04/2014

Patients who experience acute toxicity Posterior Prob[toxicity rate >20%]	5 5 0	5 7 0	5 9 0	5 1 1 0
2070]	8	7	7	7
Action	0   T	6 Cerminate e	nrollment	1

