### 7.1.2 Endpoints

### 7.1.2.1 Primary Endpoints

Feasibility will be based on multiple radiation planning and treatment parameters. For proton to be deemed feasible, no greater than 10% of patients should experience one of the following events: a) Patient cannot be given treatment because anatomy is such that a dosimetrically satisfactory treatment plan cannot be devised. For example, the dosimetry is unsatisfactory if

<95% of target volume is covered by 95% of the dose, b) Patient receives greater than 50% of their total treatment (for any reason-unable to set patient up within acceptable limits of tolerance, patient unable to tolerate treatment position or immobilization for duration of treatment) with photon beam radiotherapy (using a backup photon plan, c) Patient is unable to complete all of his/her treatments within 10 days of estimated date of treatment completion or requires a treatment break greater than 5 days.

Acute Toxicity is defined as any grade 3 or higher toxicity, considered probably or definitely related to radiation, observed within 90 days from start of therapy, excluding cranial nerve palsies or nerve root symptoms as these may be due to the tumor itself or prior surgery. Toxicities will be graded using the NCI Common Terminology Criteria for Adverse Events (CTCAE) Version 4.0.

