#### 7.1.2.2 Secondary Endpoints

Late toxicity is defined as any grade 3 or higher toxicity, considered probably or definitely related to radiation, observed later than 90 days from completion of therapy excluding cranial nerve palsies or nerve root symptoms as these may be due to the tumor itself or prior surgery. Late toxicities will be graded according to the CTCAE version 4.0. The time frame for late toxicity is open-ended and late toxicities have been known to occur a year or more after therapy. Follow-up for late toxicity will cease when a patient experiences disease progression, since 2nd line therapies may then be initiated.

Progression-free and overall survival are defined as the time from start of radiotherapy to first documented progression (local or distant event for PFS), death due to any cause or last patient contact alive. The local control rate (i.e., local progression only) may also be evaluated.

Fatigue will be scored by the Brief Fatigue Inventory (BFI), a validated instrument, which will be evaluated at the following time points: Pre-radiation, during treatment, at the inspection visit, and at approximately 3, 6, 9, 12 months post-radiation and then every 6 months for years 2 and 3, and yearly for year 4 and 5. It is expected that BFI score will increase (as fatigue worsens) in the first 6-12 months post-radiation and then the BFI score will decrease (as fatigue improves) at 12-24 months post-radiation.

Neurocognitive function will be assessed by the FACT-BR, which will be evaluated at preradiation, during treatment, at 3, 6, 9, 12 months post-radiation and then every 6 months.

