#### Neurologic Acute Toxicity

If the number of patients with neurologic acute toxicity equals or exceeds the number in the table, then termination will be considered as it is likely that the toxicity rate is >10%, as noted by the Bayesian posterior probabilities.

Bayesian Rule for Neur	ologic Acu	te Toxicity	7			
Patients treated	1	2	3	4		
	5	5	5	5		
Patients who experience acute toxicity	3	5	6	7		
Posterior Prob[toxicity rate >10%]	0	0	0	0		
7 10/0]	6	8	7	7		
	8	2	9	7		
Action	T	Terminate enrollment				

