The Principal Investigator or her designee of the trial will present to the Medical Monitor all adverse events observed inpatients, any activity data obtained, and whether those data invoked any stopping criteria in the clinical protocol. Adverse event reporting will follow the NCI guidelines. Results of the data from toxicology or other animal studies that are relevant will be discussed. Other information related to the safety and efficacy of the clinical study will be discussed. This includes information of similar investigational materials used in different studies.

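### Section 7.2.1 rules out early stopping in Phase II, but 7.2.3 sets acute-toxicity termination rules for that phase and 8.4 refers to them

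*Combined protocol and SAP*

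**What the plan says.** Section 7.2.1 sets out the Phase II design: 38 patients added to the first 12, for a total of 50, to describe toxicity and fatigue and to estimate progression-free survival. It then states: "There will be no early stopping in this phase of the study".

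Section 7.2.3 is headed as a continuation of the rules in 7.1.3 and has two tables. For non-neurologic events: "If the number of patients with non-neurologic acute toxicity equals or exceeds the number in the table, then termination will be considered". The counts are 5, 7, 9 and 11 events at 15, 25, 35 and 45 patients, against a 20% limit. The neurologic rule begins "If the number of patients with neurologic acute toxicity equals or exceeds the number in the table", with counts of 3, 5, 6 and 7 at the same looks, against a 10% limit. The action row of both tables is to end enrolment.

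Section 8.4 sends the reader to Section 7 for the stopping rules of both the feasibility phase and Phase II. Under Internal Safety and Compliance in Section 8.5, the investigator must tell the Medical Monitor "whether those data invoked any stopping criteria in the clinical protocol".

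**The concern.** One section says Phase II has no early stopping, and another gives the numbers at which stopping is to be considered. Neither is marked as superseded. The sentence in 7.2.1 is not limited to efficacy or futility, so a reader would have to supply that limit.

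The conflict has a practical consequence. The report to the Medical Monitor must say whether any stopping criterion was met. Under 7.2.1 the Phase II answer is always no, because there are none. Under 7.2.3 it depends on the counts. If a count is reached, the team could cite either section for continuing or for pausing. What is at stake is whether the acute safety rules still apply once the feasibility phase ends.

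**Working it through.** **Inputs.** The beta(1,5) prior and the looks at 3, 6, 9 and 12 come from 7.1.3. There the counts are 2, 2, 3, 4 (non-neurologic) and 1, 1, 2, 2 (neurologic). The looks at 15, 25, 35 and 45 and their counts come from 7.2.3. Section 7.2.1 includes the first 12 patients in Phase II, so the counts are cumulative.

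**Step 1: reproduce the plan's figures.** With x events in n patients, the posterior probability that the rate exceeds the limit L is P(p > L), where p follows Beta(1 + x, 5 + n − x).
- Non-neurologic, L = 0.20. At 5/15 the posterior is Beta(6,15), which gives 0.804. At 7/25, 9/35 and 11/45 it is 0.761, 0.732 and 0.711. The printed values are 0.80, 0.76, 0.7 (second decimal not legible) and 0.71, so they reproduce.
- Neurologic, L = 0.10. At 3/15, 5/25, 6/35 and 7/45 it is 0.867, 0.927, 0.900 and 0.878. The printed values are 0.68, 0.82, 0.79 and 0.77. These match one event fewer at each look (2/15, 4/25, 5/35, 6/45 give 0.677, 0.825, 0.794, 0.770). The table's counts and posteriors therefore disagree by one event. The steps below use the printed counts, because the rule is written on counts.

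**Step 2: the four 7.2.3 looks alone.** Treat each patient as an independent Bernoulli(p) outcome. Carry the binomial distribution of the running count from look to look, remove the part at or above the boundary, and add up what was removed.

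**Step 3: given that 7.1.3 was passed.** Phase II opens only after feasibility and safety are established (Section 7.2), so a high rate will often have been caught earlier. Let S1 be the probability of crossing no 7.1.3 limit for the same toxicity, and S2 the probability of crossing neither a 7.1.3 nor a 7.2.3 limit. The conditional prompt rate is 1 − S2/S1.

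For neurologic events S1 can be checked by hand. Passing needs no event in the first 6 patients and at most one in the next 6. At p = 0.10, S1 = 0.9^6 × (0.9^6 + 6 × 0.1 × 0.9^5) = 0.5314 × 0.8857 = 0.471. The same recursion gives S2 = 0.429, so the prompt rate is 1 − 0.429/0.471 = 0.088.

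| Toxicity | True rate | 7.2.3 alone | S1 | S2 | Given 7.1.3 passed |
|---|---|---|---|---|---|
| Neurologic | 5% | 4.2% | 0.711 | 0.707 | 0.5% |
| Neurologic | 10% | 27.9% | 0.471 | 0.429 | 8.8% |
| Neurologic | 20% | 87.4% | 0.172 | 0.063 | 63% |
| Non-neurologic | 10% | 2.1% | 0.872 | 0.866 | 0.7% |
| Non-neurologic | 20% | 39.0% | 0.592 | 0.457 | 23% |
| Non-neurologic | 30% | 88.0% | 0.314 | 0.084 | 73% |

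The last column comes from unrounded S1 and S2.

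**Step 4: the same quantity under 7.2.1.** With no stopping criteria in Phase II, the probability of a count-based prompt is 0 at every true rate.

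**The case against.** The strongest reply is that no one would be misled. The heading of 7.2.3, its two full tables and 8.4 all point one way, and a single sentence points the other. That sentence follows the remark on estimating progression-free survival, so it may have been meant only to exclude efficacy or futility stopping. This is the likely intent, and it makes this a drafting correction. It does not remove the conflict: the text does not limit the sentence, and it sits in the section that defines the design.

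A reader might infer that Phase II would run without safety control. The documents do not support that. SAEs go to the DSMC within 30 days (8.3.2). The Medical Monitor reviews all adverse events and may recommend suspension or termination, and summaries reach the DSMC quarterly (8.5). The tables themselves say only that termination will be considered. Only the count-based prompt disappears.

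A reader might also infer that a late-toxicity boundary is missing and must be added. The written rules do count acute events only, and such an event "is defined as any grade 3 or higher toxicity, considered probably or definitely related to radiation, observed within 90 days from start of therapy". Late toxicity is that "observed later than 90 days from completion of therapy", and 7.1.2.2 notes that "late toxicities have been known to occur a year or more after therapy". But late events pass through the same oversight, and 7.1.3 already permits the calculation for other times, "although the Bayesian probability of an event may be calculated at any time during the trial". The documents also give no basis for a limit: Section 1.1 offers only ungraded complication figures (5-10%, 13%, 9 of 45). The choice of limit decides how such a rule behaves. As an illustration, assume a beta(1,5) prior, a posterior cut-off of 0.85, and looks when 11, 23 and 31 patients have 12 months of follow-up. At a true late rate of 20%, a review is then prompted in 81%, 39% or 12% of trials for limits of 10%, 15% or 20%. Whether to add such a rule is for the sponsor to judge.

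**Conclusion.** The contradiction is real and the sentence in 7.2.1 is wrong as written. Followed literally, it cancels the Phase II acute-toxicity rules. For a cohort that has passed 7.1.3, that gives up a prompt with a probability of about 63% at a true neurologic rate of 20% and 73% at a true non-neurologic rate of 30%. At the acceptable limits themselves (10% and 20%) the figures are about 9% and 23%. Medical Monitor and DSMC oversight is unaffected.

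The conditional figures assume a 12-patient feasibility cohort, independent patients, a constant rate, and 7.1.3 limits applied as stops. Section 7.1.4 now describes 26 patients in the feasibility analysis. If Phase II opens only after those 26, the looks at 15 and 25 fall before it, and these figures do not apply as they stand. The neurologic figures also rest on the printed counts. If the printed posteriors are the correct entries, the counts drop by one, and the looks taken alone prompt in about 18% and 54% of trials at true rates of 5% and 10%. None of this affects the contradiction, which rests on the wording alone.

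**What to change.** In 7.2.1, replace the sentence on early stopping with: *Enrolment in this phase is subject to the early-termination rules in 7.2.3.* Sections 7.2.3 and 8.4 need no change for this point. If the sponsor also wants to exclude efficacy or futility stopping, a separate clause can say so.

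The cost is one sentence in an amendment, with no new visits, data, analyses or committee. The tables already exist, so the chance of an unnecessary pause is the one they already carry.

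Optional, and not part of the correction: the sponsor may wish to record whether a late-toxicity review count was considered, and why none was set.
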